# Tracking Physical Activity for Chronic Pain Management Among Older Adults in Detroit

## A. Background and Rationale

Improving function by increasing daily activity is a key goal of cognitive behavioral therapy (CBT) for pain. Incorporating wearable physical activity monitors into the design of cognitive behavioral pain self-management programs provides just-in-time data on patient progress that can be used to individualize behavioral messages and inform goal-setting. The 2016 National Pain Strategy encourages the use of wearable monitors as a pain self-management tool. Activity monitoring is likely to be most convenient for older adults when they can use accessible, commercial-grade monitors and cell phones. However, much remains unknown about how best to integrate these devices into behavioral interventions for specific groups of vulnerable older adults.

The goal of this study is to collect preliminary data regarding wearable monitor use by primarily African American older adults in Detroit in preparation for a trial of a community-based CBT intervention for chronic pain. Findings from the proposed study will inform the design of this future intervention, helping to ensure that it is effective and feasible in the Detroit community setting, and establishing a strong foundation for future competitive proposals. This is a high-priority population given the sharply disproportionate disease burden among older adults in Detroit and race disparities in pain treatment. Facilitators and barriers to activity monitor use in this population will be assessed and the feasibility and validity of various strategies for reporting daily step count data will be tested. This study is also known as the **STEPS (Seniors Tracking Exercise for Pain Self-management)**

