*Intervention group:* Intervention group participants will monitor and report step count data daily for six weeks, after which they will complete a telephone follow-up survey. For the first two-week period, a random half of the intervention group participants will receive IVR calls and half SMS messages; for the second two weeks these groups will ‘switch’; and all intervention group participants will be asked to use the automatic sync feature for the final two weeks of the six-week period.

The commercially-available Fitbit Zip™ pedometer and activity tracker can be attached to the participant’s waistband, belt, shirt, or stowed in his/her pocket. The Fitbit wirelessly syncs data from the tracker to the Fitbit software, or through an app compatible with most smartphones. The software is free for download on both Macs and PCs. Study staff will provide the activity tracker at an orientation session and assist with downloading the software including creation of a study-specific user name for downloading step count data. The participant will be asked to not add identifiable information to the Fitbit site during the course of the study.

Participants will be instructed to wear their pedometer during waking hours, except showering, bathing, or swimming, every day throughout their enrollment in the study. At any time if the participant has questions regarding the use of the pedometer or problems uploading step counts, a study staff member can be contacted by phone to assist. Study staff will retrieve users’ step

count data in three different ways, using each mode for a 2-week period (for a total of 6 weeks wearing the Fitbit and reporting data) as described below:

- *Manual upload:* Participants will be asked to use the display on their FitBit to view and then manually input daily step counts via daily IVR calls they will receive at evening times convenient to them. If the initial IVR call is missed, the system will try again 15 minutes and one hour later. For the SMS mode, participants will designate the time of evening they would like to receive their daily text. A second text will be sent one hour later if there is no response to the first.

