- *Automatic upload:* As described above, the research assistant will instruct participants in how to set up the FitBit so that data *automatically uploads* to the intervention website. Note that during this set-up process, the devices will be paired with a study account, and the email address provided will belong to the study. The information provided to the Fitbit company during set-up will not be identifying. It will include a study username, a masked birthdate (01/01/birth year plus or minus a constant), and a height and weight that is the male or female average, as appropriate.

*Control group:* Control group members will not track their steps during the study period, but will participate in baseline and follow-up data collection, after which they will receive a FitBit to keep.

Data collection:

Data will be collected via telephone by a trained research assistant at baseline and following the 6-week intervention.

Measures:

*Primary outcomes:*

Adherence to reporting will be indicated by the proportion of days with successfully logged step-counts, i.e., reported days/14 total days for each of the three reporting modes.

Pain interference: 4-item subscale from the PROMIS-29 Adult Profile, measured at baseline and follow-up.

*Secondary outcomes:*

Physical functioning: 4-item subscale from the PROMIS-29 Adult Profile, measured at baseline and follow-up.

Social participation: 4-item subscale from the PROMIS-29 Adult Profile, measured at baseline and follow-up.

Validity of manually-reported step counts will be assessed by comparing up to one month of IVR or SMS- collected data to data collected by syncing the device. Validity of the data will also be

assessed by examining associations between step data and relevant baseline characteristics (e.g., functioning scores, comorbidities, and age).

*Other baseline survey measures* (to characterize sample and/or as potential moderators of adherence and outcomes): *Demographics and health*: age, gender, education, race/ ethnicity, marital status, health literacy, comorbidities, cognitive functioning, physical activity. *Pain-related*: pain duration, number and location of pain sites, pain treatments, pain centralization. *Technology-related*: attitudes toward technology, eHealth literacy, social support for technology use.

*Staff burden*: Number of participant calls to the study technical support line, time spent giving technical assistance, and difficulties encountered as described in staff notes.

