#### Statistical Analysis Plan

Descriptive statistics will be calculated for baseline variables, comparing intervention and control groups using independent-sample t tests for continuous variables and chi-square tests for categorical variables, and on survey items related to satisfaction, acceptability, and adherence to step count reporting.

*Step data collection adherence:* (Days provided/14 days anticipated) among the three intervention modes, within and across subjects;

*Validity of manual step reports:* Proportion of days/21 days that manually-collected (SMS and IVR) and FitBit-stored counts are within 50 steps of each other will be calculated.

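### Validity of manual step reports is planned as one proportion pooled over IVR and SMS, so it cannot show which mode is more accurate, and days without a synced count have no stated handling

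*Combined protocol and SAP*

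**What the plan says.** Two weeks of IVR and two weeks of SMS come first. C. Methods (Intervention group) randomises which comes first: "a random half of the intervention group participants will receive IVR calls and half SMS messages; for the second two weeks these groups will ‘switch" over. Then "all intervention group participants will be asked to use the automatic sync feature for the final two weeks of the six-week period". Adherence in each mode is counted over 14 days.

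The reference for manual reports is defined in C. Methods (Measures, secondary outcomes) as "comparing up to one month of IVR or SMS- collected data to data collected by syncing the device". The Statistical Analysis Plan turns this into the proportion of days, out of 21, on which "manually-collected (SMS and IVR) and FitBit-stored counts are within 50 steps of each other". It lists no result by mode and no rule for manual days that lack a device count.

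On purpose, A. Background and Rationale says that "the feasibility and validity of various strategies for reporting daily step count data will be tested". Aim 2b in B. Specific Aims is narrower and speaks of manual reports as a whole.

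On set-up, C. Methods says "Study staff will provide the activity tracker at an orientation session and assist with downloading the software", and that "during this set-up process, the devices will be paired with a study account". No section says when the device counts for weeks 1-4 are retrieved.

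**The concern.** The study is meant to inform the design of a later trial, and one thing it could inform is which manual reporting mode to use. The randomised crossover supplies a within-person comparison of IVR and SMS accuracy. A single pooled proportion leaves that comparison out.

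The pooled figure is also not fully defined. The denominator of 21 does not match the number of manual days. The comparator depends on syncing, which is itself one of the behaviours under study. Whether a day with a manual report but no synced count is left out or scored as a failure changes what the proportion measures: reporting accuracy among people who synced, or a mixture of reporting accuracy and sync success.

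**Working it through.** **1. The plan's own figure.** Inputs: two manual modes and 14 days per mode (C. Methods); 21 days (Statistical Analysis Plan).

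- Manual days: 2 x 14 = 28. One mode: 14. Neither gives 21, and the documents do not explain the figure.
- Because 21 > 14, at least 21 - 14 = 7 days must come from the second of the two modes, so the statistic is necessarily pooled. If 21 days are used, the modes could contribute unequally within a person, for example 14 and 7.
- The upper limit of one month in C. Methods is compatible with 28 days. The 21 in the analysis plan is the figure that does not fit.

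**2. What a pooled proportion says about each mode.** Pooled agreement = (agreeing IVR days + agreeing SMS days) / (IVR days + SMS days). I fixed the total of agreeing days and listed the extreme splits that fit it. The totals are illustrative.

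| Days per mode | Agreeing days | Pooled | Extreme splits that fit |
|---|---|---|---|
| 14 + 14 | 17 of 28 | 61% | 3/14 = 21% with 14/14 = 100%, or the reverse |
| 14 + 14 | 20 of 28 | 71% | 6/14 = 43% with 14/14 = 100%, or the reverse |
| 14 + 14 | 25 of 28 | 89% | 11/14 = 79% with 14/14 = 100%, or the reverse |
| 14 + 7 | 15 of 21 | 71% | 8/14 = 57% with 7/7 = 100%, or 14/14 = 100% with 1/7 = 14% |

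These are bounds, not predictions. They show that the pooled value alone does not rank the modes.

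**3. Days without a synced count.** The documents give no sync rate or agreement rate, so these are assumptions: 80% agreement in those who sync; a share s of the 30 monitored participants sync, from 50% to 100%; true agreement in the rest is q, from 30% to 80%.

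- Unsynced days dropped: 80% whatever s is.
- True value in all 30: s x 0.80 + (1 - s) x q.
- Unsynced days kept as disagreement: s x 0.80.

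| s (n of 30) | Dropped | True, q = 30% | True, q = 50% | True, q = 80% | Kept as disagreement |
|---|---|---|---|---|---|
| 100% (30) | 80% | 80% | 80% | 80% | 80% |
| 90% (27) | 80% | 75% | 77% | 80% | 72% |
| 80% (24) | 80% | 70% | 74% | 80% | 64% |
| 50% (15) | 80% | 55% | 65% | 80% | 40% |

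At s = 50% and q = 30%, dropping overstates by 80 - 55 = 25 points. At s = 50% and q = 80%, keeping understates by 80 - 40 = 40 points. The direction depends on a rule that the plan does not give.

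**The case against.** **Aim 2b asks only about manual reports as a whole, and the mode of every manual day is known.** Both points are right. A pooled figure answers Aim 2b, and by-mode agreement can be calculated at any time from the same data. The limitation belongs to the planned statistic, not to the data. The Background's commitment to test the various strategies still goes unmet in the analysis plan.

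**A reader might infer that device counts for weeks 1-4 come only from a sync first used in weeks 5-6**, so that anyone who stops early has no comparator. The documents do not support this. Weeks 5-6 are when sync becomes the reporting mode. Software download and account pairing belong to set-up with staff help, so earlier or background syncing is possible. The documents are silent on when counts are retrieved.

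**A reader might also infer that late syncing erases first-mode days.** That needs a device retention limit, and none is given. If the device held M days, a first sync on day d would recover days d - M to d - 1. At the scheduled start of the sync period, day 29, M = 30 recovers all 28 manual days and M = 21 recovers 21 (7 + 14). A first sync on day 42 would recover 17 (3 + 14) and 8 (0 + 8). Loss is possible under some assumptions and absent under others.

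**Nor can agreement be called biased upward.** That requires unsynced days to be dropped and unsynced people to report less accurately. A fixed denominator could push the figure down instead.

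Finally, this is a secondary outcome in a preliminary study with 30 monitored participants, which limits how much weight the point can carry.

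**Conclusion.** The point holds in two parts.

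First, the planned validity statistic is pooled over IVR and SMS and cannot rank them, despite a randomised crossover and a stated intent to test the various strategies. This follows from the documents alone. The mismatch between 21 days and 28 manual days also stands without any assumption.

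Second, the comparator exists only where a sync succeeded, and neither the timing of retrieval for weeks 1-4 nor the handling of unsynced days is stated. The result may be distorted in either direction. The size, up to 25 points too high or 40 points too low in the cases shown, rests entirely on the assumed rates and vanishes if everyone syncs.

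The documents do not establish a late-sync design, a loss of first-mode days, or a known direction of bias.

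**What to change.** In the Statistical Analysis Plan, under validity of manual step reports:

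- Calculate agreement, with the existing 50-step margin, separately for IVR and SMS. For each mode use manual-report days that have a synced count, up to 14.
- Report the within-person IVR-SMS difference.
- Keep the pooled value, over up to 28 days, in place of 21.
- Exclude days without a synced count from the denominator, and report by mode how many participants and days lack one. Exclusion does not remove selection, but the counts let a reader judge how far it could matter.
- State when and how device counts for weeks 1-4 are retrieved. Staff can download them from the study account where they have already synced.

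This costs a few sentences and a short table, with no new data collection. Asking participants for extra syncs before week 5 is a different matter. It could recover more comparator days, but it gives practice in the third mode, and adherence in that mode is part of a primary outcome. Any such prompt should be weighed against that effect.

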#### Data security and management

##### *Staff training to ensure confidentiality, security, and adherence to protocol*

All members of the study team will be required to complete the University of Michigan's web-based Responsible Conduct of Research Training Program (PEERRS) and to sign a confidentiality document stating that they understand the procedures to be followed to ensure the integrity and confidentiality of the data and the consequences of disregarding them.

Research staff will sign a pledge of confidentiality and will understand that breach of confidentiality is reason for dismissal. Training of staff will include information about the importance of privacy and confidentiality and techniques to maintain confidentiality of all information.

Regular study team meetings will be used to ensure that all data quality and IRB policies and procedures are being followed. This will include ensuring that (1) all participants understand, agree to, and sign a written consent form before participating; (2) strict adherence is maintained to communication regarding the participants' right to withdraw or refuse to answer questions; (3) staff maintain confidentiality both by protecting hard-copy and electronic data collection forms and also by avoiding all unauthorized conversations about individual patients; (4) consent forms and identifying information are kept separately from study related information about patients' sociodemographics, clinical characteristics, disease self-care, service use, and outcomes; and (5)

all identifying information is kept locked at all times and sensitive computer files are maintained on a secured University of Michigan server.

#### *Study participant information: REDCap*

All study participant data will be collected, stored and managed in REDCap. REDCap is a secure, web-based application designed to support data capture for research studies, providing 1) an intuitive interface for validated data entry; 2) audit trails for tracking data manipulation and export procedures; 3) automated export procedures for seamless data downloads to common statistical packages; and 4) procedures for importing data from external sources. It is HIPAA compliant and supported by the University of Michigan. (See additional information below in *Data Management Protocol* section.)

#### *IVR/SMS platform security*

Secure servers (virtual machines) at Michigan Medicine will host the IVR/SMS platform, store the participants' contact data and responses, and send out automated IVR calls and SMS messages to patients. Information stored on the participants includes first and last name, a telephone number, date of birth, and a study ID. An instance of Microsoft Dynamics CRM 2016 (industry standard CRM) will store the patient information, schedule and execute phone calls/SMS sessions, and store participant responses which will be retained until the end of the study. All information passing in and out of the IVR system is encrypted using SSL. We understand that SMS is inherently unsecure; to mitigate this, we will only collect step counts and will not use identifying language in the SMS questions.

CRM access control is managed through LDAP using Level-2 accounts from the University of Michigan. Outside vendors do occasionally access the system to perform upgrades or troubleshooting, using Level-2 UM accounts and Remote Desktop Protocol. These servers cannot be accessed from outside the Michigan Medicine network – off-site connections require use of a VPN. They are backed up daily to allow for quick system recovery with minimal data loss in case of disaster. They are separate from Electronic Health Records, and the CRM website is the only place at which patient information can be directly accessed. All Michigan Medicine servers are actively monitored to detect attacks, potential attacks, and unauthorized use.

#### *Information about Fitbit data accessed*

Per the FitBit Terms of Service and Privacy Policy, Fitbit accesses height, weight, gender and age to estimate calories; and contact information. Note that in our study, when we are setting up participants' devices, we will provide a study email, not the participant's personal email. We will not be providing a name; we will use a study identifier. To mask birth year, we will provide the same birthday – 1/1- for everyone and will add or subtract a constant from the birthyear. We will input an average male or female height and weight with the permission of the participant. In sum, no personally identifying information will be provided to the company.

Note that all data collected from the FitBit device belongs to the user, not Fitbit. Upon user request, they will deactivate the account and all data associated with that account will be deleted, including backups.

#### *Data Management Protocol*

A REDCap database will be set up to contain all participant data, including identifying information. After training regarding issues of confidentiality, only specially designated research staff will be authorized to have password-secured administrative access to the master list of names and original participant data. All other research staff and health educators will only have access to specific and select information on an “as needed” basis in order, e.g., to collect interview data, conduct the intervention or mail gift card incentives. This level of access will also be password secured to just those few individuals who need the data. Otherwise, participants’ data records will have only a sequential code number necessary for identification.

Data management personnel will prepare the data entry software, and will set up the logical and range checks. This software will store the data, together with the date of entry, in a data entry set that will be maintained in the research office at the School of Public Health.

Written documentation of data collection, storage, and transmission procedures will be maintained by the data management personnel.

#### Statistical Analysis Plan

Descriptive statistics will be calculated for baseline variables, comparing intervention and control groups using independent-sample t tests for continuous variables and chi-square tests for categorical variables, and on survey items related to satisfaction, acceptability, and adherence to step count reporting.

*Step data collection adherence:* (Days provided/14 days anticipated) among the three intervention modes, within and across subjects;

*Validity of manual step reports:* Proportion of days/21 days that manually-collected (SMS and IVR) and FitBit-stored counts are within 50 steps of each other will be calculated.

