## B. Specific Aims:

1. Identify 50 adults, predominantly African American, age > 60 years with chronic musculoskeletal pain. Thirty of these participants will be randomly assigned to receive a FitBit Zip™ and instructions for reporting daily step-count data in 3 ways (2 weeks each of manual via Interactive Voice Response (IVR) telephone calls, manual via SMS (text messaging), automatic (via syncing the device with an app) (n=30); or to a control group (n=20).
2. After a six-week monitoring period: a) compare step data collection adherence (days provided/days anticipated) among the three intervention modes, within and across subjects; b) assess the validity of manual step reports by comparing them with device-stored data; and c) compare changes in functional outcomes between monitoring and control groups.

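### The validity statistic divides by an undefined 21 days, although manual reporting lasts 28 days, and taken literally it counts unreported days as inaccurate ones

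*Combined protocol and SAP*

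**What the plan says.** Aim 2b in Specific Aims is to "assess the validity of manual step reports by comparing them with device-stored data". The Statistical Analysis Plan turns this into one statistic: "Proportion of days/21 days that manually-collected (SMS and IVR) and FitBit-stored counts are within 50 steps of each other will be calculated".

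The rest of the document describes the period in these terms:

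- Specific Aims, Aim 1, sets the reporting modes at "2 weeks each of manual via Interactive Voice Response (IVR) telephone calls, manual via SMS (text messaging), automatic" sync making up the third.
- Methods, Intervention group, gives the order: "For the first two-week period, a random half of the intervention group participants will receive IVR calls and half SMS messages". The halves then swap for the next two weeks, and everyone uses automatic sync for the last two.
- Methods, Secondary outcomes, describes the validity check as "comparing up to one month of IVR or SMS- collected data to data collected by syncing the device".
- Methods, Primary outcomes, defines adherence separately as "reported days/14 total days for each of the three reporting modes". The adherence line of the analysis plan uses the same 14.

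**The concern.** The figure of 21 days matches no period in the schedule, and no section defines it. Two analysts could therefore compute different results from the same data.

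The fixed denominator raises a second and more serious problem. A day without a manual report, or without a device-stored count, cannot meet the 50-step criterion. It adds nothing to the numerator but keeps its place in the denominator, so it is treated exactly like a wrong report. The figure then falls when participants skip reports, even if every report they gave was accurate.

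Aim 2b asks about accuracy. Non-reporting already has its own primary outcome. The study is meant to inform a later trial, where skipped reports and inaccurate reports would call for different changes to the design. The statistic as written cannot tell them apart.

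**Working it through.** **Step 1: can 21 be reproduced from the schedule?**

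Inputs: two weeks (14 days) per mode, three modes, two of them manual (Specific Aims; Methods, Intervention group).

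- One mode: 14 days.
- Both manual modes: 14 + 14 = 28 days.
- All three modes: 3 × 14 = 42 days.
- One month (Methods, Secondary outcomes): about 28 to 31 days, stated as an upper limit.

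None of these is 21. The number appears only through constructions that the documents do not describe, such as half of 42 or one and a half modes.

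**Step 2: what range can the statistic take?**

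- *Reading 1, all 28 manual days may enter the numerator.* The result passes 100% at 22 agreeing days (22/21 = 104.8%) and can reach 28/21 = 133.3%.
- *Reading 2, an unstated 21-day subset.* The maximum is 100%, but the days are unknown. If the first 21 consecutive days were meant, for example, each participant would contribute 14 days of the first mode and 21 − 14 = 7 of the second. Which mode dominated would then depend on the randomised order.

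**Step 3: how does the statistic depend on missing days?**

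Let *a* be the share of days that have both counts and *v* the agreement on those days.

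- Reading 1: 28 × a × v / 21
- Reading 2: 21 × a × v / 21 = a × v
- Paired-day denominator: v

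Reading 1 equals *v* only when 28a/21 = 1, that is a = 21/28 = 75%. Reading 2 equals *v* only when a = 100%.

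The documents give neither *a* nor *v*. The table assumes v = 90% and varies *a*:

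| Days with both counts (a) | Reading 1 | Reading 2 | Paired days |
|---|---|---|---|
| 50% | 60% | 45% | 90% |
| 75% | 90% | 67.5% | 90% |
| 90% | 108% | 81% | 90% |
| 100% | 120% | 90% | 90% |

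For example, at a = 50%, reading 1 is 28 × 0.5 × 0.9 / 21 = 12.6/21 = 60%, and reading 2 is 0.5 × 0.9 = 45%. True agreement is the same in every row, and only the last column recovers it throughout.

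**The case against.** The best defence is that 21 was never meant to be the length of manual reporting. The Secondary outcomes text sets an upper limit of a month, and a 21-day comparison fits within it. A statement that two counts lie within 50 steps also presupposes that both exist, so the authors may have intended to compare only days with both. On that view the plan omits a detail but contains no error. It is also fair to say that reading 1 is the less natural one, since a proportion should not exceed 100%, and that the percentages in the table rest on assumed inputs. Finally, this is a descriptive secondary measure in 30 monitored participants, with no test or decision rule attached.

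Part of this stands. A 21-day window is not impossible under the schedule; it is undefined. The results above 100% are the weaker part of the case, and the percentages show how the formula behaves rather than what this study will find.

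The paired-days defence does not rescue the line. The adherence line just above it in the analysis plan uses the same form, days achieved over a fixed number of days, and there the fixed denominator is meant to penalise missing days. Nothing tells the analyst to treat the next line differently. If only days with both counts were intended, dividing by 21 is correct only for a participant who has exactly 21 of them.

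**Conclusion.** The concern holds. The denominator of 21 days cannot be derived from the 28 scheduled manual days, and no section defines it. Followed as written, the rule scores an unpaired day as disagreement, so the Aim 2b figure reflects adherence as well as accuracy.

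The day counts and the ceiling of 133.3% under reading 1 follow from the documents alone. The size of the distortion depends on how many days have both counts, which the documents do not give. With 90% agreement assumed and 50% to 100% of days paired, the reported figure would run from 45% to 90% under reading 2 and from 60% to 120% under reading 1.

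The consequence is limited to the interpretation of a secondary descriptive measure. The primary outcomes, the sample size and error rates are not affected. It should still be fixed, because it is the only line of the analysis plan that sets out the device comparison Aim 2b asks for.

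**What to change.** In the Statistical Analysis Plan, replace the division by 21 days with division by the number of days on which both a manual report and a device-stored count exist. At most 28 days per participant can qualify. Report the number of paired days beside the proportion, so that readers can see how much data supports it. Showing IVR and SMS separately, with at most 14 days each, is optional. Leave non-reporting to the adherence outcome.

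If 21 days was chosen for a practical reason, such as how much stored device data can be retrieved, state the reason and the days covered, and still divide by the paired days within that window.

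The cost is one line of wording and a changed denominator in the code. No new data are needed.

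### The validity analyses cannot show whether days without a manual report differ in step level from reported days, and the 21-day denominator is undefined and does not match the 28 manual days

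*Combined protocol and SAP*

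**What the plan says.** Section B (Specific Aims), aim 2b, is to "assess the validity of manual step reports by comparing them with device-stored data". Three planned analyses bear on this.

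- **Agreement.** The Statistical Analysis Plan sets a proportion of days with 21 as its denominator, for which the match between "manually-collected (SMS and IVR) and FitBit-stored counts are within 50 steps of each other will be calculated". SMS and IVR are named together, and no separate result for each is specified. The Measures part of section C describes the same check as "comparing up to one month of IVR or SMS- collected data to data collected by syncing the device".
- **Association.** Measures adds that validity will also be "assessed by examining associations between step data and relevant baseline characteristics", such as functioning, comorbidity and age. It does not say whether the step data are manual or device counts.
- **Adherence.** This primary outcome is "reported days/14 total days for each of the three reporting modes".

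On the design, section C has staff collecting step counts "using each mode for a 2-week period", with IVR and SMS as the two manual modes. Participants are told to wear the device daily while enrolled. Repeat calls and a repeat text are planned for missed prompts, so days without a report are foreseen.

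**The concern.** Agreement within 50 steps needs two numbers. A day with no manual report has only one at most, and the plan does not say whether such a day is a failure, is excluded, or falls outside the 21. The reader of the result could not tell a mode with inaccurate reports from one with missing reports.

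The second difficulty remains however the denominator is defined. The device is to be worn on unreported days too, so it may hold counts for them, yet nothing in the plan sets those counts against the counts on reported days. If people tend to miss prompts on unusually quiet days, or on unusually active ones, the submitted numbers can each be correct while their mean misrepresents the person's activity.

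The Background says that monitoring "provides just-in-time data on patient progress that can be used to individualize behavioral messages and inform goal-setting", and that the findings will inform a later intervention. A manual mode used for that purpose would need a mean that represents usual activity as well as accurate individual entries.

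**Working it through.** **1. The denominator.** Two manual modes at 14 days each give 2 × 14 = 28 manual days. The SAP's 21 is not reproduced, and no derivation is given. With 28 accurate reports, 28/21 = 1.33, which is not a proportion. The one-month limit in Measures is compatible with 28 days but does not explain 21.

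**2. What the proportion returns when days are skipped and every report is exact.**

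- Fixed 21-day window, unreported days as failures: 7 skipped gives 14/21 = 67%; 14 skipped gives 7/21 = 33%.
- Reported days only: 100% at any skip rate.
- Agreeing days among all 28, divided by 21: 7 skipped gives 21/21 = 100%.

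**3. Can it separate random from step-dependent skipping?** The documents give no skip rate or accuracy, so assume that a share *s* of days is skipped and that 95% of reported days agree, whatever the step level. The expected values are:

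| Reading | Formula | *s* = 0.25 | *s* = 0.40 |
|---|---|---|---|
| Reported days only | 0.95 | 0.95 | 0.95 |
| Fixed window of 21 (or all 28), unreported = failure | 0.95(1 − *s*) | 0.71 | 0.57 |
| Agreeing days from 28, divided by 21 | 0.95(1 − *s*) × 28/21 | 0.95 | 0.76 |

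The step level of the skipped days appears in no formula. A simulation of 30 participants over 28 days (1,000 runs, assumed mean of 4,000 steps, within-person coefficient of variation 0.3 to 0.6) gave these same values for random and for low-step-dependent skipping.

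Reported days/14 counts the missing days but not their steps. The associations relate step data to baseline traits that are fixed for each person. From device counts they do not involve the reports at all; from manual counts they contain only reported days. Neither version shows how a person's skipped days differ from the others.

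**4. Possible size.** Let *a* be the share of days reported and *r* the ratio of mean steps on unreported to reported days. The relative error of the reported mean is 1/(*a* + (1 − *a*)*r*) − 1.

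- *a* = 0.7, *r* = 0.7: 1/0.91 − 1 = +9.9%.
- *a* = 0.9, *r* = 0.9: 1/0.99 − 1 = +1%.
- *a* = 0.6, *r* = 0.5: 1/0.80 − 1 = +25%.
- *a* = 0.7 with the ratio inverted, *r* = 1/0.7 = 1.43: 1/1.129 − 1 = −11.4%.

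In the simulation, low-step-dependent skipping (log-odds slope 1 or 2 per within-person SD) overstated the mean by 6% to 19% with 25% of days skipped, and by 10% to 29% with 40% skipped. Random skipping gave 0%. All these inputs are assumed.

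**5. Would the added comparison see it?** In the same simulation, a paired test of each person's mean device steps on reported minus unreported days rejected in 4% to 5% of runs under random skipping and in about 100% under step-dependent skipping. This used both modes together, complete device data and no partial non-wear. Fourteen days per mode, with real gaps, would be less precise.

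**The case against.** The strongest case against the point has five parts.

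- **Aim 2b concerns the accuracy of submitted numbers, and aim 2a covers completeness.** Missing reports are not hidden, because adherence by mode is a primary outcome. This stands. However, adherence shows how many days are missing and not what kind of days they were.
- **A reader might infer that validity is judged only on reported days, so that a mode could show full agreement while overstating steps.** The documents do not support this. The SAP writes a fixed count of 21 days, and if unreported days are failures, skipping lowers the score. It also specifies no validity result by mode.
- **A reader might infer that participants skip their low-step days.** Eligibility requires chronic pain that interfered with usual activities, which makes this plausible, but nothing shows that it happens. A prompt missed on a busy day would bias the mean downward. The direction is open.
- **The remedy has limits.** No wear-time measure is described, so a low device count on an unreported day may reflect a partly worn device. The documents also do not say that device counts for every unreported day will be retrieved. Both stand, and must be stated with the result.
- **The associations are a supplement, and validity is a secondary outcome of a preliminary study.** This stands and limits the weight of the point. The plan does not claim that an association measures agreement with the device.

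**Conclusion.** The point holds in two parts. First, the validity proportion is not fully defined: 21 conflicts with the 28 manual days, and the scoring of days without a report is unstated. Identical data with exact reports can give 67% or 100% depending on the reading. This rests on the documents alone.

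Second, no planned analysis can show whether unreported days differ in step level from reported ones, so a bias in the mean of manual reports, in either direction, would pass undetected. That gap is also a matter of what the plan contains. Its numerical size is not: about 10% too high is an illustration under assumed inputs, with +1% to +25% over the upward scenarios and negative values if active days are the ones missed.

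The point does not show that manual reports are biased, or that the planned proportion would make a poor mode look accurate. It is a low-cost improvement that changes what the trial can conclude about manual reporting, and it leaves the rest of the trial unaffected.

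**What to change.** In the Statistical Analysis Plan:

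1. Reconcile the 21-day denominator with the 28 manual days and with the window in Measures. Report agreement within 50 steps per manually reported day with available device data, separately for IVR and SMS, and report missing reports as their own figure.
2. Where device counts are retrieved, report by mode with 95% CIs: (a) the within-person difference in device-stored steps between reported and unreported days; (b) each person's mean of manual reports minus the mean of all device-stored days in the same period.
3. Show zero-count device days separately. State that partial non-wear may explain low counts on unreported days, and that the results cover only days with retrieved device data.
4. Label the associations with baseline characteristics as descriptive, and say which step data they use.

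The cost is SAP wording and one small table, with no new measurements on participants. People who report every day contribute nothing to 2(a), and without a wear-time measure a difference there can be described but not fully explained.
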